5 STUDY PROCEDURES

All patients will be evaluated as outlined in Study Calendars (See [ATTACHMENT A](#)). Dosing, laboratory tests, imaging studies and office visits/telemedicine will occur per protocol (within ± 4 days) unless patients' medical or logistical issues necessitate adjustment.

5.1 Pretreatment Evaluations

To be completed within 4 weeks prior to initiation of therapy:

- Medical history, including list of current medications
- Imaging studies with CT scans of chest, abdomen and pelvis
- Tumor markers, CA125 and/or CA15.3
- ECHO or MUGA, and then as clinically indicated
- A copy of microsatellite stable (MSS) and FGFR1-4 aberration (activating mutations or amplification) as pre-identified in a Clinical Laboratory Improvement Amendments (CLIA)-certified laboratory
- A comprehensive ophthalmological examination, including optical coherence tomography (OCT) of the macula, prior to initiation of therapy, every 2 months for the first 6 months, and every 3 months thereafter
- Informed consent signed by patient and investigator

To be completed within 7 days of initiation of therapy:

- Physical exam including symptoms and signs
- ECOG performance status (See [ATTACHMENT B](#))
- Complete blood count with leukocyte differential and platelet count
- Serum chemistries including sodium, potassium, chloride, carbon dioxide, BUN, creatinine, glucose, calcium, phosphate, magnesium, albumin, alkaline phosphatase, total bilirubin, AST, ALT, TSH and free T4
- ECG
- Urinalysis
- Tumor markers, CA125 and/or CA15.3 if elevated at screening
- Women of childbearing potential will have a pregnancy test using blood

5.2 On Study Evaluations

To be obtained weekly during the initial 3 weeks and then as clinically indicated:

- Complete blood count and leukocyte differential and platelet count
- Serum chemistries including sodium, potassium, chloride, carbon dioxide, BUN, creatinine, glucose, calcium, phosphate, magnesium, albumin, alkaline phosphatase, total bilirubin, AST and ALT
- Physical exam including symptoms and signs

ECOG performance status

To be obtained at the beginning of each subsequent cycle:

- Medical history and physical exam
- ECOG performance status
- Assessment of treatment-related and -unrelated toxicities
- Complete blood count with leukocyte differential and platelet count
- Serum chemistries including sodium, potassium, chloride, carbon dioxide, BUN, creatinine, glucose, calcium, phosphate, magnesium, albumin, alkaline phosphatase, total bilirubin, AST, ALT, TSH and free T4
- ECG
- Urinalysis
- Tumor markers, CA125 and/or CA15.3 if elevated at screening
- Women of childbearing potential will have a pregnancy test using blood
- A comprehensive ophthalmological examination, including optical coherence tomography (OCT) of the macula, prior to initiation of therapy, every 2 months for the first 6 months, and every 3 months thereafter will be performed. For onset of visual symptoms, refer patients for ophthalmologic evaluation urgently, with follow-up every 3 weeks until resolution or discontinuation of futibatinib.

To be obtained once every 6-9 weeks for tumor measurement:

- Evaluation of tumor: the same imaging technique or more sophisticated studies will be performed once every 6 weeks of therapy (6 weeks \pm 7 days) for the initial 12 weeks after starting the treatment, and then once every 9 weeks (9 weeks \pm 7 days), or sooner as clinically indicated

Patients will be seen by a physician at the start of treatment and then prior to initiating subsequent cycles (+/- 7 days). In order to more precisely determine time of progression [more precisely](#), the investigator is encouraged to obtain radiological assessments earlier if there is a strong clinical suspicion of progression of disease to either confirm or refute the clinical impression. Possible adverse events will be discussed in detail with each patient and assessed on a continuing basis. ECG, echocardiogram, and other radiological-laboratory tests will be monitored throughout treatment if clinically indicated.

Ophthalmological Examination

The cornea and conjunctiva are readily visible tissues, and therefore, abnormalities of the cornea and conjunctiva can usually be recognized via external ocular examination and routine slit lamp biomicroscopy. The retina is visible through fundoscopy after dilation of the pupil. Ophthalmologic examination will be performed by a trained ophthalmologist or qualified delegate.

A comprehensive ophthalmological examination, including optical coherence tomography (OCT) of the macula, prior to initiation of therapy, every 2 months for the first 6 months, and every 3 months thereafter will be performed. For onset of visual symptoms, refer patients for ophthalmologic evaluation urgently,

Each evaluation will encompass:

- External ocular examination
- Routine slit lamp biomicroscopy of anterior ocular structures, including the anterior and posterior chambers (Fluorescein or rose Bengal or other dyes used to evaluate the ocular surface can be used according to institutional guidelines and local clinical practice)
- Dilation of the pupil with direct/indirect fundoscopy per institutional guidelines and local clinical practice
- OCT

[figure not shown]
Patient-Reported Outcome (PRO) Measurement Tools (optional)

Patients will be instructed to capture symptomatic adverse events weekly for the initial 6 weeks after starting the treatment (cycle 1 and 2), and at the end of each cycle (subsequent cycles) thereafter through paper, online and/or portal device according to Patient-Reported Outcomes version of the Common Terminology Criteria for Adverse Events (PRO-CTCAE™ <https://healthcaredelivery.cancer.gov/pro-ctcae>), and the 2-level version of EQ-5D (EQ-5D-3L: <https://euroqol.org/eq-5d-instruments/eq-5d-3l-about/>).

5.3 Translational Research

Exploratory Objectives: To identify plasma and tissue biomarkers associated with response to futibatinib and pembrolizumab in patients with metastatic microsatellite stable (MSS) endometrial carcinoma.

Rationale: Growing evidence suggests that activation of FGFR induces macrophage recruitment and cytokine production, leading to protumorigenic alterations via tumor immunosuppressive microenvironment ^{56,57}. Moreover, preclinical studies demonstrate that combination therapy of lenvatinib (VEGF/FGFR inhibitor) with PD-1 blockade improved cancer immunotherapy by reducing TAMs and enhancing antitumor activity via the IFN signaling pathway⁷¹. FGFR pathway inhibition, increased T-cell infiltration, decreased regulatory T cells, and downregulation of PD-L1 expression on tumor cells ⁶⁶. However, mechanisms underlying this combination effects of futibatinib and pembrolizumab in endometrial cancer are unknown. TCGA data revealed that high expression of FGFR3 is significantly correlated with poor survival in endometrial cancer ($p<0.001$). In addition, preliminary data using the ImmGen database revealed that FGFR1 is highly expressed in macrophages and FGFR2-4 are expressed on stromal cells (Figure 8).

On the basis of the compelling preclinical and pilot clinical data, we hypothesized that *dynamic changes in TAM-related biomarkers and inflammatory cytokines will be associated with response to futibatinib and pembrolizumab in patients with metastatic endometrial carcinoma*. Our translational endpoints will be to assess plasma markers (inflammatory cytokines/chemokines) and tissue markers (M2-like and M1-like markers, MDSCs, CD8, CD25, CD34, CD56), and pAKT, pERK2, FGFR1-4, PD-L1, and PD-1 at baseline, within 1 week prior to cycle 2 day 1 (C2D1), and at time of relapse in patients who have displayed stable disease (SD) \geq 6months, CR or PR (SD \geq 6months/CR/PR).

Pre- and post-biopsy tissues will be used for monitoring dynamic changes in macrophages (with phenotype of M2-like CD markers, and MHCII), and CD4/CD8, MDSCs, NK, and T-regs using multiplex IHC. PBMCs will be used for monitoring dynamic gene changes in classical (CD14+/CD16-) and non-classical monocytes (CD14low/CD16+) by RNA sequencing. NGS will be utilized on tumor specimens and cfDNA for targeted exome panel including FGFR1-4 genetic aberrations at baseline, within 1 week prior to cycle 2 day 1 (C2D1), and at time of relapse in patients who have displayed SD≥6months/CR/PR.

Sample Collections

For purposes of collecting blood and tumor samples, the Investigational Cancer Research services (ICRS) at MD Anderson will provide bulk tubes and reagents for PD and biopsies, tube labels, and subject requisition forms.

Blood sample collections:

After the informed consent is obtained, 20 mL blood will be collected into CPT tubes at each of the following time-points (optional): prior to the initiation of treatment (pre-study), prior to the initiation of cycle 2 day 1 (C2D1), and at end of therapy if available or prior to cycle 13 day 1 (C13D1) if still on therapy. PBMCs will be collected for RNA sequencing. Plasma will be collected for multiplex ELISA and DNA NGS.

Blood samples will be collected in green-topped Vacutainer tubes containing sodium heparin. Plasma at 0.5-1 mL/vial and peripheral blood mononuclear cells (PBMCs) will be isolated and cryopreserved in 10% DMSO and 90% human AB serum at 10×10^6 cells/vial and stored at -70°C to -80°C until later analysis ([name] at Gynecologic Oncology).

Tumor sample collections:

After informed consent is obtained, tumor core biopsy samples will be collected as follows:

1. Ten 5- μ m thick FFPE slides, or tumor block – all patients
2. Pre-treatment core biopsy – all patients if archival samples are not available
3. Tumor core biopsy within 1 week before C2D1 – 12 patients at stage II
4. After-study tumor core biopsy at time of relapse in patients who have displayed SD≥6months/CR/PR – optional

The time of drug administration and the time of biopsy will be documented. The treating physician, principal investigator, and interventional radiologist will work together to ensure that patients will not be subject to a significant risk procedure for the purpose of obtaining tissue for this study. In particular, a significant risk procedure is generally considered to be one for which the procedure associated absolute risk of mortality or major morbidity in the patient's clinical setting and at the institution completing the procedure, is 2% or higher. Procedures more invasive than a core biopsy are not utilized. The core biopsies will be snap frozen and stored in cryogenic storage tubes. The sample should be frozen by total immersion in liquid nitrogen or an alcohol dry-ice bath and kept in liquid nitrogen or an alcohol dry-ice bath or buried in dry ice pellets from the time of freezing until the time of storage in the -70°C to -80°C freezer ([name] at Gynecologic Oncology). Part of the biopsies will be formalin-fixed paraffin-embedded (FFPE) for IHC and pathologic diagnosis.

Sample processing

Samples may be processed and tested as designed or via a more sophisticated technique when available:

1. Cytokine and chemokine measurement using Multiplex ELISA at baseline, prior to C2D1, at end of therapy if available or prior to C13D1 if still on therapy.
2. Multiple IHC on tumor specimens at baseline (all), prior to C2D1 (patients at stage II), and at relapse in patients with documented SD \geq 6months/CR/PR.
3. NGS on circulating DNA at baseline, prior to C2D1, at end of therapy if available or prior to C13D1 if still on therapy.
4. NGS on tumor specimens for targeted exome panel including FGFR1-4 genetic aberrations to reveal potential biomarkers at baseline (all), prior to C2D1 (patients at stage II), and at relapse in patients with documented SD \geq 6months/CR/PR.

Methods: To assess the utility of surrogate biomarkers and the anti-tumor response to therapy with the combination treatment of futibatinib and pembrolizumab in patients with metastatic endometrial cancer, we will draw 20 ml blood for plasma markers (inflammatory cytokines/Chemokines) and PBMC RNA sequencing and cfDNA NGS, prior to the initiation of cycle 2 day 1 (C2D1), and at end of therapy if available or prior to cycle 13 day 1 (C13D1) if still on therapy. The biopsied tissues will be used for DNA extraction for NGS using exome panel including FGFR1-4 genetic aberrations, and multiplex IHC for monitoring dynamic changes in M2 like macrophages (with phenotype of M2-like and M1-like CD markers), and CD4/CD8, MDSCs, NK, and Treg.

Multiplex ELISA for detecting cytokines/chemokines. 5 ml blood will be drawn for detecting both human inflammation cytokines/chemokine panels in plasma collected at baseline, prior to C2D1, at end of therapy if available or prior to C13D1 if still on therapy. Plasma will be collected, aliquoted and stored at -80°C for further processing. Multiplex ELISA will be performed on the manufacturer's instruction⁷⁹.

Tumor biopsy and tumor marker analysis: Core needle biopsy will be performed in the Diagnostic Imaging Department at baseline if archival tumor tissues are not available, prior to the initiation of cycle 2 day 1 (C2D1), and at relapse in patients with documented SD \geq 6months/CR/PR (optional). Sample will be frozen for detecting surface markers of M2-like macrophages, CD4/ CD8, MDSCs, NK and Treg cells by multiplex IHC at the Pathology Core at MDACC⁸⁰. Freshly frozen tumor samples will be analyzed for FGFR1-4 mutations by NGS at the Genomic core at MDACC.

Detection of monocyte- and CD8-enriched genes in PBMCs: 5 ml blood will be collected into CPT tubes at baseline, prior to C2D1, at end of therapy if available or prior to C13D1 if still on therapy. PBMCs will be collected and frozen and stored at -80°C for further processing. RNA will be extracted from PBMCs obtained from these patients before and after treatment. RNA sequencing will be carried out for detecting monocyte- and CD8-preselected genes in PBMCs⁸¹.

cfDNA NGS: 10 ml blood will be collected into CPT tubes at baseline, prior to C2D1, at end of therapy if available or prior to C13D1 if still on therapy. Utilizing the quick-cfDNA serum/plasma Kit (Zymo Research), DNA will be extracted from plasma obtained from these patients before and after treatment and stored at -80°C for further DNA sequencing [82-84](#). [82-84].

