9. Ability to read and fully understand the requirements of the trial, willingness to comply with all trial visits and assessments, and willingness and ability to sign an institutional review board (IRB)-approved written informed consent document.
10. Any prior radiation must have been completed at least 14 days prior to the start of study drugs, and patients must have recovered from any acute adverse effects prior to the start of study treatment (Radiotherapy for extended field within 4 weeks or limited field radiotherapy within 2 weeks).
11. Ability to take oral medications without medical history of malabsorption or other chronic gastrointestinal disease, or other conditions that may hamper compliance and/or absorption of the study agents (feeding tube is not permitted).
12. Provision of an archival tissue block, or 10 formalin-fixed paraffin-embedded (FFPE) slides obtained within 6 months prior to study entry; or agreeing to have biopsies if archival tissues are not available.

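### Section 5.3 gives two preparations for the biopsy used in multiplex IHC; if it is frozen, the change from an archival FFPE baseline mixes preparation with treatment

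*Combined protocol and SAP*

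**What the plan says.** **Baseline tissue.** Criterion 12 in Section 3.1 asks for "Provision of an archival tissue block, or 10 formalin-fixed paraffin-embedded (FFPE) slides obtained within 6 months prior to study entry", with consent to a biopsy as the alternative. The tumor collection list in Section 5.3 starts with ten slides or a block from everyone ("thick FFPE slides, or tumor block – all patients") and then gives the fallback: "Pre-treatment core biopsy – all patients if archival samples are not available". Footnote l of Attachment A repeats this order.

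**On-treatment tissue.** The same list has a core biopsy in the week before C2D1 in the 12 stage II patients, and an optional one at relapse after a response or lasting stable disease. The text below the list has cores snap frozen, and then adds: "Part of the biopsies will be formalin-fixed paraffin-embedded (FFPE) for IHC and pathologic diagnosis". The Methods part of Section 5.3 says: "Sample will be frozen for detecting surface markers of M2-like macrophages, CD4/ CD8, MDSCs, NK and Treg cells by multiplex IHC". For tumor sequencing (NGS) it says: "Freshly frozen tumor samples will be analyzed for FGFR1-4 mutations by NGS at the Genomic core at MDACC".

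**Planned use.** The sample-processing list in Section 5.3 has IHC and tumor NGS at baseline in all patients, before C2D1 in stage II patients, and at relapse. The translational hypothesis is that changes over time in macrophage-related markers go with response. Section 7.2 analyses longitudinal biomarker data with a mixed model that has patient effects, and assigns the signed-rank test to continuous variables in general. No section requires the same preparation at each time point, plans a bridging check, or puts preparation in the model.

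**The concern.** A within-patient change can be read as a treatment effect only if the two measurements differ in nothing else that is systematic. If the first sample is FFPE and the second is frozen, any difference in how the two preparations stain enters the change with the same sign in each affected patient. The laboratory has to choose a preparation when the core arrives, and the protocol gives it two answers for IHC. If it chooses frozen, the mismatch may be impossible to undo in the analysis. At stake is the interpretability of research biopsies taken from up to 12 patients.

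**Working it through.** The plan gives no figure on this point, so there is none to reproduce. The check has four parts.

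**1. Readings of Section 5.3.**
- Methods text taken literally: multiplex IHC compares an FFPE baseline with a frozen C2D1 core in each patient with archival tissue. NGS has the same mismatch.
- FFPE part of the core used for multiplex IHC: the IHC comparison is FFPE against FFPE, and the mismatch remains for NGS only.
- FFPE part meant for a separate conventional IHC: the two statements no longer conflict, but the multiplex IHC mismatch stands.

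On every reading, an archival FFPE baseline cannot meet the Methods requirement for freshly frozen NGS input.

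**2. Number of pairs.** Twelve is a ceiling. Exact binomial sums for the Section 7.1 rule (stop if fewer than 3 of 12 respond) match the early-stopping figures in Table 11: 73.58% at a response rate of 15% and 8.34% at 40%. Stage II, and so any C2D1 biopsy, is therefore reached with probability 100 − 73.58 = 26.42% and 100 − 8.34 = 91.66% respectively.

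**3. Can the model separate preparation from time?** Take 12 patients with two samples each, and columns for 12 patient effects, time and preparation (14 in all), with every C2D1 sample frozen.
- 12 of 12 baselines archival: preparation equals time in every row. The rank is 13 for 14 columns, so the two effects cannot be separated.
- 10 or 6 of 12 archival: the rank is 14, so they can be separated, but only if preparation is in the model. With fixed patient effects, only the 12 − 10 = 2 or 12 − 6 = 6 fresh-baseline pairs then estimate the time effect.

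**4. Illustrative size.** Let a be the number of archival baselines among 12 pairs and s the preparation shift, in SDs of the paired difference. The documents give neither; both are assumptions. With no drug effect, the bias in the mean change is (a/12) × s. For a = 6 and s = 0.5 it is 0.5 × 0.5 = 0.25 SD; for a = 12 and s = 0.5 it is 0.5 SD.

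The exact two-sided signed-rank test with 12 pairs has a true level of 4.2% at nominal 5%. Rejection rates with no drug effect (normal differences, 200,000 simulated trials per cell):

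| Archival baselines | s = 0.25 | s = 0.5 | s = 1 |
|---|---|---|---|
| 6 of 12 | 5.6% | 9.7% | 23.4% |
| 8 of 12 | 6.8% | 14.7% | 41.8% |
| 10 of 12 | 8.6% | 22.0% | 65.1% |
| 12 of 12 | 10.8% | 31.5% | 85.1% |

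**Association with response.** The bias in the difference in mean change between responders and non-responders is s × (archival share in responders − archival share in non-responders). It is zero if all baselines are archival, or if the shares are equal. With a mix, the shift also adds variance s² × f × (1 − f), where f is the archival share. For s = 0.5 and f = 0.5 this is 0.25 × 0.25 = 0.0625, against a variance of 1 for the paired difference.

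**The case against.** The strongest reply is that Section 5.3 describes a split core, part frozen and part FFPE, and that the laboratory would naturally use the FFPE part for IHC. That is possible, and it is the arrangement recommended below, but the Methods text says the opposite for the multiplex panel.

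A second reply is that the change analysis is meant only for pairs of core biopsies, with archival tissue used for description. This does not fit the sample-processing list, which has IHC on baseline tumor from all patients. It would also leave only patients without archival tissue in the paired set.

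A third reply stands. The stated hypothesis is about association with response, and a shift common to all pairs cancels there. The bias falls on the mean change. The association is biased only if preparation differs by response; otherwise a mix of baselines adds noise.

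A reader might also infer more than the documents support:
- That most baselines will be archival. Archival tissue is the default, but no share is given.
- That the signed-rank test would give p = 2/4096, about 0.0005. That is the smallest value attainable with 12 pairs. It needs every pair to move the same way, and is not an estimate of anything here.
- That NGS should move to FFPE because Section 5.3 already provides for it. The FFPE part is set aside for IHC and diagnosis, not for sequencing.
- That pairs whose baseline predates the last therapy must be excluded. No section says when archival tissue was taken relative to that therapy, and with at most 12 pairs an exclusion could cost more than it gains.

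**Conclusion.** The point holds as a low-cost improvement to an exploratory analysis. The two statements in Section 5.3 on tissue for IHC need to be reconciled. If the frozen route is followed, the mean change in macrophage and immune markers is confounded with preparation for each patient with an archival baseline, and completely so if all baselines are archival. The baseline-to-relapse comparison, where that optional biopsy is taken, has the same problem. The magnitude cannot be taken from the documents: the range of about 6% to 32%, against 4.2%, rests on an assumed shift of 0.25 to 0.5 SD and 6 to 12 archival baselines. Patients with a fresh baseline core can have matched tissue. Response rate, safety and the go/no-go rule are not touched.

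**What to change.** - **IHC.** In the Methods part of Section 5.3, run the paired multiplex IHC on the FFPE part of each core at every time point, in line with the collection text.
- **Records and main analysis.** Record preparation and collection date for each specimen. In Section 7.2, limit the main change analysis to pairs with the same preparation.
- **Tumor NGS.** Correct the requirement for freshly frozen input, which archival baselines cannot meet. State the input for each time point and flag mixed-preparation pairs; FFPE need not be required.
- **Prior therapy.** Show the change results by whether the baseline tissue predates the last systemic therapy, as a sensitivity analysis and not as an exclusion.

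The cost is wording in Sections 5.3 and 7.2 and two data fields per specimen, with no extra biopsy. The downside is that part of a small core is committed to FFPE, and the laboratory must confirm that the multiplex panel works on FFPE tissue.
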